### **2.3.4. Site Inspections**

Site visits will be conducted by the Sponsor or an authorized representative for inspection of study data, participants' medical records, and eCRFs. The Investigator will permit national and local Health Authorities, Sponsor monitors, representatives, and collaborators, and the IRBs/ECs to inspect facilities and records relevant to this study.

### **3. STUDY AND SITE CLOSURE**

The Sponsor (or designee) has the right to close the study site or terminate this study at any time. Reasons for terminating the study may include, but are not limited to, the following:

- The incidence or severity of adverse events in this or other studies indicates a potential health hazard to participants.
- Participant enrollment is unsatisfactory.

The Sponsor will notify the Investigator and Health Authorities if the study is placed on hold, or if the Sponsor decides to discontinue the study or development program.

Study sites will be closed upon study completion. A study site is considered closed when all required documents and study supplies have been collected and a study-site closure visit has been performed.

The Investigator may initiate study-site closure at any time, provided there is reasonable cause and sufficient notice is given in advance of the intended termination.

Reasons for the early closure of a study site by the Sponsor or Investigator may include but are not limited to:

- Failure of the Investigator to comply with the protocol, the requirements of the IRB/IEC or local Health Authorities, the Sponsor's procedures, or GCP guidelines.
- Inadequate recruitment of participants by the Investigator.
- Discontinuation of further study treatment development.

## **Appendix 2**

### **Adverse Events: Definitions and Procedures for Evaluating, Follow-up and Reporting**

#### **1. DEFINITION OF ADVERSE EVENTS**

According to the E2A ICH guideline for Good Clinical Practice, an **adverse event** is any untoward medical occurrence in a patient or clinical investigation subject administered a pharmaceutical product and which does not necessarily have to have a causal relationship with this treatment.

An adverse event can therefore be:

- Any unfavorable and unintended sign (including an abnormal laboratory finding), symptom, or disease temporally associated with the use of a medicinal product, whether or not considered related to the medicinal product.

#### **Events Meeting the AE Definition:**

- Any deterioration in a laboratory value (hematology, clinical chemistry, or urinalysis) or other clinical test (e.g., ECG, X-ray) that is associated with symptoms or leads to a change in study treatment or concomitant treatment or discontinuation from study treatment.
- Exacerbation of a chronic or intermittent pre-existing condition, including either an increase in frequency and/or intensity of the condition.
- New conditions detected or diagnosed after study treatment administration even though it may have been present before the start of the study.
- Adverse events that are related to a protocol-mandated intervention, including those that occur prior to assignment of study treatment (e.g., screening invasive procedures such as biopsies).

#### **Events NOT Meeting the AE Definition:**

- Any clinically significant abnormal laboratory findings or other abnormal safety assessments which are associated with the underlying disease, unless judged by the Investigator to be more severe than expected for the participant's condition.
- The disease/disorder being studied or expected progression, signs, or symptoms of the disease/disorder being studied, unless more severe than expected for the participant's condition.
- Medical or surgical procedure (e.g., endoscopy, appendectomy): the condition that leads to the procedure is an AE.
- Situations where an untoward medical occurrence did not occur (social and/or convenience admission to a hospital).
- Anticipated day-to-day fluctuations of pre-existing disease(s) or condition(s) present or detected at the start of the study that do not worsen.

## 2. **DEFINITION OF SERIOUS ADVERSE EVENTS**

If an event is not an AE per definition above, then it cannot be a serious adverse event (SAE) even if serious conditions are met (e.g., hospitalization for signs/symptoms of the disease under study, death due to progression of disease).

A serious adverse event is defined as any untoward medical occurrence that at any dose:

- **Results in death.**
- **Is life-threatening.**

The term "life-threatening" in the definition of "serious" refers to an event in which the participant was at risk of death at the time of the event; it does not refer to an event which hypothetically might have caused death if it was more severe.

- **Requires inpatient hospitalization or prolongation of existing hospitalization** (see [Appendix 3](#)).

In general, hospitalization signifies that the participant has been detained (usually involving at least an overnight stay) at the hospital or emergency ward for observation and/or treatment that would not have been appropriate in the physician's office or outpatient setting. Complications that occur during hospitalization are AEs. If a complication prolongs hospitalization or fulfills any other serious criteria, the event is serious. When in doubt as to whether "hospitalization" occurred or was necessary, the AE should be considered serious.

Hospitalization for elective treatment of a pre-existing condition that did not worsen from baseline is not considered an AE.

- **Results in persistent or significant disability/incapacity**

Disability means substantial disruption of the participant's ability to conduct normal life functions.

This definition is not intended to include experiences of relatively minor medical significance such as uncomplicated headache, nausea, vomiting, diarrhea, influenza, and accidental trauma (e.g., sprained ankle) which may interfere with or prevent everyday life functions but do not constitute a substantial disruption.

- **Is a congenital anomaly/birth defect.**
- **Other significant events:**

Medical or scientific judgment should be exercised in deciding whether SAE reporting is appropriate in other situations such as important medical events that may not be immediately life-threatening or result in death or hospitalization but may jeopardize the participant or may require medical or surgical intervention to prevent one of the other outcomes listed in the above definition. These events should usually be considered serious.

Examples of such events include invasive or malignant cancers, intensive treatment in an emergency room or at home for allergic bronchospasm, blood dyscrasias or

convulsions that do not result in hospitalization, or development of drug dependency or drug abuse.

### **3. RECORDING OF ADVERSE EVENT AND/OR SERIOUS ADVERSE EVENT**

When an AE/SAE occurs, it is the responsibility of the Investigator to review all documentation (e.g., hospital progress notes, laboratory reports, and diagnostics reports) related to the event.

The Investigator will then record all relevant AE/SAE information in the CRF.

It is **not** acceptable for the Investigator to send photocopies of the participant's medical records to Medical Monitor in lieu of completion of the eCRF.

There may be instances when copies of medical records for certain cases are requested by the sponsor. In this case, all participant identifiers, with the exception of the participant number, will be redacted on the copies of the medical records before submission to the sponsor.

The Investigator will attempt to establish a diagnosis of the event based on signs, symptoms, and/or other clinical information. Whenever possible, the diagnosis (not the individual signs/symptoms) will be documented as the AE/SAE.

#### **3.1. ASSESSMENT OF SEVERITY**

The Investigator will make an assessment of severity for each AE and SAE reported during the study and assign it to one of the categories provided in [Table 1](#) (as a guidance for assessing adverse event severity).

The terms "severe" and "serious" are not synonymous. Severity refers to the intensity of an adverse event (rated as mild, moderate, or severe, or according to a pre-defined grading criteria [e.g., National Cancer Institute Common Terminology Criteria for Adverse Events [NCI CTCAE] criteria]; the event itself may be of relatively minor medical significance (such as severe headache without any further findings).

Severity and seriousness need to be independently assessed for each adverse event recorded on the eCRF.

Serious adverse events are required to be reported by the Investigator to the Sponsor immediately (i.e., no more than 24 hours after learning of the event).

**Table 1 Adverse Event Severity Grading Scale**

Severity	Description
Mild	Discomfort noticed, but no disruption of normal daily activity
Moderate	Discomfort sufficient to reduce or affect normal daily activity
Severe	Incapacitating with inability to work or to perform normal daily activity

Note: Regardless of severity, some events may also meet seriousness criteria. Refer to definition of a serious adverse event (see above).

### **3.2. ASSESSMENT OF CAUSALITY**

Investigators should use their knowledge of the participant, the circumstances surrounding the event, and an evaluation of any potential alternative causes to determine whether or not an adverse event is considered to be related to the study treatment, indicating "yes" or "no" accordingly. The following guidance should be taken into consideration:

- Temporal relationship of event onset to the initiation of study treatment.
- Course of the event, considering especially the effects of dose-reduction, discontinuation of study treatment, or reintroduction of study treatment (where applicable).
- Known association of the event with the study treatment or with similar treatments.
- Known association of the event with the disease under study.
- Presence of risk factors in the participant or use of concomitant medications known to increase the occurrence of the event.
- Presence of non-treatment-related factors that are known to be associated with the occurrence of the event.

For participant receiving combination therapy, causality will be assessed individually for each protocol-mandated therapy.

### **4. FOLLOW-UP OF AES AND SAEs**

The Investigator is obligated to perform or arrange for the conduct of supplemental measurements and/or evaluations as medically indicated or as requested by the Sponsor to elucidate the nature and/or causality of the AE or SAE as fully as possible. This may include additional laboratory tests or investigations, histopathological examinations, or consultation with other health care professionals.

If a participant dies during participation in the study or during a recognized follow-up period, the Investigator will provide the Sponsor with a copy of any post-mortem findings including histopathology

New or updated information will be recorded in the originally completed eCRF.

The Investigator will submit any updated SAE data to the Sponsor within 24 hours of receipt of the information.

## **5. IMMEDIATE REPORTING REQUIREMENTS FROM INVESTIGATOR TO SPONSOR**

Certain events require immediate reporting to allow the Sponsor to take appropriate measures to address potential new risks in a clinical trial. The Investigator must report such events to the Sponsor immediately; under no circumstances should reporting take place more than 24 hours after the Investigator learns of the event. The following is a list of events that the Investigator must report to the Sponsor within 24 hours after learning of the event, regardless of relationship to study treatment:

- Serious adverse events
- Non-serious adverse events of special interest (NSAESI)
- Pregnancies (see [Section 8.3.5](#))
- Accidental overdoses or medication errors

The Investigator must report new significant follow-up information for these events to the Sponsor immediately (i.e., no more than 24 hours after becoming aware of the information). New significant information includes the following:

- New signs or symptoms or a change in the diagnosis.
- Significant new diagnostic test results.
- Change in causality based on new information.
- Change in the event's outcome, including recovery.
- Additional narrative information on the clinical course of the event.

Investigators must also comply with local requirements for reporting serious adverse events to the local Health Authority and IRB/EC.

### **5.1 REPORTING REQUIREMENTS OF SERIOUS ADVERSE EVENTS AND NON-SERIOUS ADVERSE EVENTS OF SPECIAL INTEREST**

#### **Events that Occur prior to Study Treatment Initiation**

After informed consent has been obtained but prior to initiation of study treatment, only serious adverse events caused by a protocol-mandated intervention should be reported. The Serious Adverse Event/Adverse Event of Special Interest Reporting Form provided to Investigators should be completed and submitted to the Serious Adverse Event Responsible immediately (i.e., no more than 24 hours after learning of the event).

## **Events that Occur after Study Treatment Initiation**

For reports of serious adverse events and non-serious adverse events of special interest ([Section 8.3.6](#)) that occur after initiation of study treatment ([Section 8.3.1](#)), investigators should record all case details that can be gathered on the appropriate Serious Adverse Event/Adverse Event of Special Interest Reporting Form provided to investigators and submit the report to the Serious Adverse Event Responsible immediately (ie no more than 24 hours after learning of the event), either by faxing or by scanning and emailing the form using the fax number or email address provided to investigators.

### **Reporting of Post-Study Adverse Events and Serious Adverse Events**

If the Investigator becomes aware of any other serious adverse event occurring after the end of the AE reporting period, if the event is believed to be related to prior study treatment the event should be reported directly to the Sponsor or its designee, either by faxing or by scanning and emailing the SAE Reporting Form using the fax number or email address provided to investigators.

## **5.2 Reporting Requirements for Cases of Accidental Overdose or Medication Error**

Accidental overdose and medication error (hereafter collectively referred to as "special situations"), are defined as follows:

- Accidental overdose: accidental administration of a drug in a quantity that is higher than the assigned dose
- Medication error: accidental deviation in the administration of a drug

In some cases, a medication error may be intercepted prior to administration of the drug.

Special situations are not in themselves adverse events, but may result in adverse events. All special situations associated with RO7017773, regardless of whether they result in an adverse event, should be recorded on the Adverse Event eCRF and reported to the Sponsor immediately (i.e., no more than 24 hours after learning of the event).

Special situations should be recorded as described below:

- Accidental overdose: Enter the drug name and "accidental overdose" as the event term. Check the "Accidental overdose" and "Medication error" boxes.
- Medication error that does not qualify as an overdose: Enter the name of the drug administered and a description of the error (e.g., wrong dose administered, wrong dosing schedule, incorrect route of administration, wrong drug, expired drug administered) as the event term. Check the "Medication error" box.
- Medication error that qualifies as an overdose: Enter the drug name and "accidental overdose" as the event term. Check the "Accidental overdose" and "Medication error" boxes. Enter a description of the error in the additional case details.

- Intercepted medication error: Enter the drug name and "intercepted medication error" as the event term. Check the "Medication error" box. Enter a description of the error in the additional case details.

For RO7017773, each adverse event associated with a special situation should be recorded separately on the Adverse Event eCRF. If the associated adverse event fulfills seriousness criteria, the event should be reported to the Sponsor immediately (i.e., no more than 24 hours after learning of the event; see [Appendix 2, Section 5.1](#)). For RO7017773, adverse events associated with special situations should be recorded as described below for each situation:

- Accidental overdose: Enter the adverse event term. Check the "Accidental overdose" and "Medication error" boxes.
- Medication error that does not qualify as an overdose: Enter the adverse event term. Check the "Medication error" box.
- Medication error that qualifies as an overdose: Enter the adverse event term. Check the "Accidental overdose" and "Medication error" boxes.

As an example, an accidental overdose that resulted in a headache would require the completion of two Adverse Event eCRF pages, one to report the accidental overdose and one to report the headache. The "Accidental overdose" and "Medication error" boxes would need to be checked on both eCRF pages.

## **6. EXPEDITED REPORTING TO HEALTH AUTHORITIES, INVESTIGATORS, INSTITUTIONAL REVIEW BOARDS, AND ETHICS COMMITTEES**

The Sponsor will promptly evaluate all serious adverse events and NSAESI against cumulative product experience to identify and expeditiously communicate possible new safety findings to investigators, IRBs, ECs, and applicable Health Authorities based on applicable legislation.

To determine reporting requirements for single adverse event cases, the Sponsor will assess the expectedness of these events using the following reference document(s):

- RO7017773 Investigator's Brochure

The Sponsor will compare the severity of each event and the cumulative event frequency reported for the study with the severity and frequency reported in the applicable reference document.

Reporting requirements will also be based on the Investigator's assessment of causality and seriousness, with allowance for upgrading by the Sponsor as needed.

## **Appendix 3** **Procedures for Recording Adverse Events**

Investigators should use correct medical terminology/concepts when recording adverse events on the Adverse Event eCRF. Avoid colloquialisms and abbreviations.

Only one adverse event term should be recorded in the event field on the Adverse Event eCRF.

### **1. DIAGNOSIS VERSUS SIGNS AND SYMPTOMS**

For adverse events, a diagnosis (if known) should be recorded on the Adverse Event eCRF rather than individual signs and symptoms (e.g., record only liver failure or hepatitis rather than jaundice, asterixis, and elevated transaminases). However, if a constellation of signs and/or symptoms cannot be medically characterized as a single diagnosis or syndrome at the time of reporting, each individual event should be recorded on the Adverse Event eCRF. If a diagnosis is subsequently established, all previously reported adverse events based on signs and symptoms should be nullified and replaced by one adverse event report based on the single diagnosis, with a starting date that corresponds to the starting date of the first symptom of the eventual diagnosis.

### **2. ADVERSE EVENTS OCCURRING SECONDARY TO OTHER EVENTS**

In general, adverse events occurring secondary to other events (e.g., cascade events or clinical sequelae) should be identified by their primary cause, with the exception of severe or serious secondary events. However, medically significant adverse events occurring secondary to an initiating event that are separated in time should be recorded as independent events on the Adverse Event eCRF. For example:

- If vomiting results in mild dehydration with no additional treatment in a healthy adult, only vomiting should be reported on the eCRF.
- If vomiting results in severe dehydration, both events should be reported separately on the eCRF.
- If a severe gastrointestinal hemorrhage leads to renal failure, both events should be reported separately on the eCRF.
- If dizziness leads to a fall and subsequent fracture, all three events should be reported separately on the eCRF.

All adverse events should be recorded separately on the Adverse Event eCRF if it is unclear as to whether the events are associated.

### **3. PERSISTENT OR RECURRENT ADVERSE EVENTS**

A persistent adverse event is one that extends continuously, without resolution, between participant evaluation time-points. Such events should only be recorded once on the Adverse Event eCRF. The initial severity of the event should be recorded, and the severity should be updated to reflect the most extreme severity any time the event worsens. If the event becomes serious, the Adverse Event eCRF should be updated to reflect this.

A recurrent adverse event is one that resolves between participant evaluation time-points and subsequently recurs. Each recurrence of an adverse event should be recorded separately on the Adverse Event eCRF.

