### **4. ABNORMAL LABORATORY VALUES**

Not every laboratory abnormality qualifies as an adverse event. A laboratory test result should be reported as an adverse event if it meets any of the following criteria:

- Accompanied by clinical symptoms.
- Results in a change in study treatment (e.g., dosage modification, treatment interruption, or treatment discontinuation).
- Results in a medical intervention (e.g., potassium supplementation for hypokalemia) or a change in concomitant therapy.
- Clinically significant in the Investigator's judgment.

It is the Investigator's responsibility to review all laboratory findings. Medical and scientific judgment should be exercised in deciding whether an isolated laboratory abnormality should be classified as an adverse event.

If a clinically significant laboratory abnormality is a sign of a disease or syndrome (e.g., alkaline phosphatase and bilirubin 5 times the upper limit of normal [ULN] associated with cholecystitis), only the diagnosis (i.e., cholecystitis) should be recorded on the Adverse Event eCRF.

If a clinically significant laboratory abnormality is not a sign of a disease or syndrome, the abnormality itself should be recorded on the Adverse Event eCRF, along with a descriptor indicating if the test result is above or below the normal range (e.g., "elevated potassium", as opposed to "abnormal potassium"). If the laboratory abnormality can be characterized by a precise clinical term per standard definitions, the clinical term should be recorded as the adverse event. For example, an elevated serum potassium level of 7.0 mEq/L should be recorded as "hyperkalemia".

Observations of the same clinically significant laboratory abnormality from visit to visit should not be repeatedly recorded on the Adverse Event eCRF, unless the etiology

changes. The initial severity of the event should be recorded, and the severity or seriousness should be updated any time the event worsens.

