17.1.1 Adverse Events

Treatment emergence will be evaluated for all AEs. Treatment-emergent adverse events (TEAE) are those which occur after the first dose of study drug.

TEAEs occurring following dosing in a specific period but before dosing in the next period will be attributed to the treatment in that period. If the time is missing for an AE on a dosing day then the AE will be attributed to the treatment given on that day.

The following missing data will be imputed as defined (for calculations only / will not be presented):

- Missing AE start and / or end times for the calculation of onset and duration will be assumed to be at 00:01 for a start time and 23:59 for end times
- Missing AE severity or relationship will be assumed to be severe or related, respectively
- Missing AE start times for the determination of treatment emergence will be assumed to occur after treatment unless partial date documents the AE as happening prior to treatment
- Missing AE start times for the determination of treatment assignment will be assumed to occur after treatment on the recorded date one minute after dosing
- Missing AE start date will be assumed to be after treatment for the determination of TEAE but will not be attributed to a specific treatment

A summary of number and percentage of subjects reporting TEAEs, TEAEs by severity and relationship, serious AEs (SAEs), and subjects who discontinued study drug due to an AE will be provided.

A summary of the number and percentage of subjects reporting each TEAE, categorized by system organ class and preferred term coded according to the Medical Dictionary for Regulatory Activities (MedDRA), will be presented by treatment and overall. Counting will be done by subject only, not by event; subjects will only be counted once within each body system or preferred term.

A summary of the number and percentage of subjects reporting each TEAE will be presented by relationship to study drugs (as recorded on the eCRF) and by treatment and overall. Subjects with multiple events within a system organ class or preferred term will be counted under the category of their most drug-related event within that system organ class or preferred term.

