A summary of the number and percentage of subjects reporting each TEAE will be presented by severity (as recorded on eCRF) and by treatment and overall. Subjects with multiple events within a system organ class or preferred term will be counted under the category of their most severe event within that system organ class or preferred term.

All AEs (including non-treatment-emergent events) recorded on the eCRF will be listed by subject.

A separate listing of AEs leading to study drug discontinuation will be provided.

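### An adverse event still ongoing at the next crossover dose that then worsens appears in the by-treatment AE tables only under the earlier treatment, at its worst severity

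*Protocol*

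**What the plan says.** The result comes from three rules, in two documents, read together.

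- **Recording (Protocol Appendix 3).** Section 3 defines the case: "A persistent adverse event is one that extends continuously, without resolution, between participant evaluation time-points". It then says: "Such events should only be recorded once on the Adverse Event eCRF". The initial severity is noted, and "the severity should be updated to reflect the most extreme severity any time the event worsens". Section 4 is similar for laboratory findings: "Observations of the same clinically significant laboratory abnormality from visit to visit should not be repeatedly recorded on the Adverse Event eCRF", with an exception where the etiology changes, and "the severity or seriousness should be updated any time the event worsens". Section 5 repeats this for vital signs.
- **Attribution (SAP 17.1.1).** "TEAEs occurring following dosing in a specific period but before dosing in the next period will be attributed to the treatment in that period". The imputation rules in the same section include one headed "Missing AE start times for the determination of treatment assignment". TEAEs are defined as events after the first dose, with no mention of worsening.
- **Tabulation (SAP 17.1.1).** "A summary of the number and percentage of subjects reporting each TEAE will be presented by severity (as recorded on eCRF) and by treatment". The table also has an overall column, and each participant is counted at the most severe event within a system organ class or preferred term. The incidence and relationship tables are also split by treatment.

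**The concern.** Recording an event once at its worst severity suits a trial in which each participant stays on one treatment. Here participants change treatment every 7 to 10 days (Protocol 4.1.2), and nothing in the recording rule makes a new dose close an open record. The whole record, with its final severity and causality, goes to the period in which it began.

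If the event worsens after a later dose, the earlier treatment is charged with a severity it did not precede. The later treatment shows nothing for that participant. Safety of the different formulations is a secondary objective (Protocol Table 6), and the AE tables are the planned display of it by treatment.

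**Working it through.** There is no stated figure to reproduce. The check traces one case through the rules and then sizes it.

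**1. Does onset decide the column?** The attribution sentence speaks of TEAEs occurring in a period, and start times are what is imputed to settle treatment assignment. Neither document offers another date. Attribution by onset is an inference, but it is the only reading that the text supports.

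**2. Does another rule catch the case?**
- The recurrent-event rule (Appendix 3 Section 3) needs resolution first, so it does not apply.
- The preexisting-condition rule (Appendix 3 Section 8) covers only conditions present at screening, so it does not reach an event that began in an earlier period.
- The changed-etiology exception (Appendix 3 Sections 4 and 5) covers laboratory and vital-sign findings only. Neither document says that another dose of the same drug is such a change.
- The TEAE definition has no worsening component.

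**3. Worked case.** Take sequence ABCD (SAP 6.2). A mild event starts after A in Period 1, does not resolve, and becomes severe after B in Period 2.

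| Output | Rules as written | New record dated at the worsening |
|---|---|---|
| Incidence, A | 1 participant | 1 participant |
| Incidence, B | 0 | 1 participant |
| Severity, A | 1 severe | 1 mild |
| Severity, B | 0 | 1 severe |
| Relationship | one causality, under A | own causality under each of A and B |
| Overall column | 1 participant, severe | 1 participant, severe |

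**4. Size of one case.** Percentages use participants exposed within a treatment (SAP 9.1.4). The planned numbers are 16 in Part 1 and 8 in Part 2 (SAP 6.0).
- Part 1: 1/16 = 6.25 points. If only 12 received that treatment, 1/12 = 8.3 points.
- Part 2: 1/8 = 12.5 points.

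In the severity table this amount leaves the severe row of the later treatment and enters that of the earlier one. In the incidence table the later treatment is short by this amount and the earlier one is unchanged.

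**5. Where it can happen.** Only a dose that follows an earlier dose can be involved.
- Part 1: 16 × 3 = 48 of 16 × 4 = 64 planned doses.
- Part 2: 8 × 1 = 8 of 8 × 2 = 16 planned doses.

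These are opportunities, not expected cases. The event must still be ongoing 7 to 10 days after the previous dose, and the documents give no AE rate from which to estimate how often that occurs.

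**6. Direction.** The four Part 1 sequences contain each of the 12 ordered adjacent treatment pairs exactly once. With equal allocation, the opportunities for misplacement into the preceding treatment are spread evenly over the other three treatments. The design does not steer the error towards one formulation, but balance does not correct an individual case.

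**The case against.** Much of the case against is sound and limits the point.

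- **A reader might infer that the worsening is hidden.** It is not. Laboratory values, vital signs and mean ECG parameters are summarised for each treatment and time point (SAP 17.1.3 to 17.1.5). AEs, SAEs and AEs leading to discontinuation are listed by participant. With 16 and 8 participants these listings can be read individually. A symptom, however, has no second by-treatment display.
- **A reader might infer that the first severity is lost.** Appendix 3 asks for the initial severity too. If the eCRF keeps both, the increase is captured. The eCRF is not among the documents, and the SAP does not say which severity its table would then use. Appendix 3 also asks for no date of worsening, so the SAP alone may be unable to reassign the event.
- **A reader might take a persisting enzyme elevation as the typical case.** That is a weak example. Table 5 places the eligibility review and chemistry on Day -1, under the heading for each period, and exclusion criteria 12 and 13 concern laboratory abnormalities at Day -1. The documents do not spell out the consequence in later periods, but redosing cannot simply be assumed. Protocol 8.2.4 also calls for immediate repeat testing of unexplained clinically significant values.
- **A reader might double the figures**, to 12.5 points (Part 1) and 25 points (Part 2), as the change in a between-treatment difference. No such AE comparison is planned and no hypothesis is tested (Protocol 9.1, SAP 9.4.3).
- **A reader might infer that an event stopping a participant under Protocol 4.1.3 would be missed.** It would be in the discontinuation listing; only its table column would be wrong.

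What remains is that the stated rules, followed as written, put the event in the wrong column, and no other rule moves it.

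**Conclusion.** The point holds for the by-treatment AE incidence, severity and relationship tables, and only for those. An event ongoing at a later dose that then worsens is shown only under the treatment of onset, at its worst severity. Overall incidence, overall worst severity, PK, the by-treatment laboratory, vital-sign and ECG summaries, and the listings are unaffected.

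One case is worth 6.25 points in Part 1 and 12.5 points in Part 2. Cases should be few.

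The conclusion rests on four assumptions:
- onset decides attribution, as the start-time rules imply;
- the severity table uses the updated severity;
- a further dose is not treated as a change of etiology;
- the eCRF guideline, which is not available here, does not already split such records.

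The change is worth making because the rules produce a wrong table entry and correcting them is cheap. It does not threaten the study's primary conclusions.

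**What to change.** Two additions:

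1. **Protocol Appendix 3 Sections 3 to 5, or the eCRF completion guideline.** As an exception to single recording: if an ongoing event increases in severity or becomes serious after dosing in a later period, enter a new record linked to the first. Date it at the worsening and give it its own severity and causality. The first record keeps its pre-worsening severity.
2. **SAP 17.1.1.** State that the new record is attributed to the treatment of the period in which the worsening began, and that the first record stays with its own treatment.

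The recording rule should be settled before data are collected, because a date of worsening that was never recorded may not be recoverable at analysis.

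The cost is one sentence in each document and one extra record per affected event. The same continuing event will count under two treatments, which a table footnote can explain. Counting is by participant, so the overall column still counts that participant once. No dosing or stopping rule changes.
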